## 3. Phase III (Long Term Follow up):

Subjects who achieve protocol-defined clinical benefit from treatment in Phase I or Phase II will be followed for 6 months after treatment.

If a subject experiences re-emergence of depressive symptoms, an acute TMS retreatment course will be initiated. The TMS retreatment course will continue up to 6 weeks until symptom score is at or below Phase III entry score. Each successful retreatment is followed by a 3-week taper. Subjects could receive retreatment on more than one occasion; therefore, any subject could receive up to 72 treatments in Phase III over 6 months, in addition to Phase I and II exposure.

44-02219-204, Rev C 21-JAN-2019

Page 8 of 28

#### B. Schedule of Events:

[from adolescent study protocol Appendices A, B, and C]

#### Phase I:

Phase	1-Wee Prestud						3-Week Post-Treatment Ta				
Week	Wk –2 to -1° (Screening)	Wk 0 a (Baseline)	Wk 1 b	Wk 2 b	Wk 3 b	Wk 4 b	Wk 5⁵	Wk 6 5,c /ET	Wk 1	Wk 2	Wk 3
Day(s)	-7ª	0°	1-5	8-12	15-19	22-26	29-35	36-42	43-49	50-56	57-63
Informed Consent/Assent/HIPAA	x										
Psychiatric/Medical History/TASS	x										
Antidepressant Treatment Record (ATR)	x										
M.I.N.I. / M.I.N.I. KID	x										
Pre/Post-TEEQ-P d		x						x			
Pre/Post-TEEQ-A		x						x			
Efficacy Assessments e											
HAMD 24 /MADRS f	x	х				X d		Xc,e			X°
CDRS-R	x	х				Xď		Xc'e			X°
CGI-S	x	х				Xď		Xce			Xe
QIDS-A17-SR	x	х				X d		Xc,e			Xe
Neuropsychological Assessments e											
NIH Toolbox Cognition Battery		х						Xc,e			
Safety Assessments											
Physical examination	x										
Vital Signs		х						Xc			
YMRS°		х									
C-SSRS e	x	х	Xe	Xe	Xe	Xe	Xe	Xc,e	Xe	Xe	X°
Laboratory determinations 	x										
Urine drug screen	x										
Pregnancy test h	x										
Structural MRI	x							x			
Audiometry assessment		x						Xc			
Adverse Events i		х							Х		
Prior/Concomitant Treatment k		Х							Х		
Motor Threshold Determination 	X i										
TMS Treatment Session b (daily × 5 weekdays/week)			XX b	XX b							
Post-Treatment Taper TMS Session(s) m (3X/Wk1, 2X/Wk 2, 1X/Wk 3)									x	x	x

A minimum of 7 days may elapse between the screening and baseline visits; a maximum of 5 days may elapse between the baseline visit and the first treatment day of Week 1. All baseline a. assessments must be completed and laboratory results received before 1st TMS treatment.

The first visit during each week of treatment should occur on a Monday, with daily treatment sessions occurring on Monday through Friday of each week. b.

Subjects who prematurely discontinue should complete all Week 6 procedures within 2 days after their last TMS treatment session. c.

d.

If subject <18 yrs of age or the legal age requirement of the state Efficacy, neuropsychological and safety assessments to be performed after last TMS treatment session on last day of the treatment week when assessments are required. Y-MRS to be completed e. if symptom indicating mania occurs. If positive, a M.I.N.I./M.I.N.I. KID must be repeated to determine if subject meets full DSM-5 criteria for mania or hypomania. If positive, subject to be discontinued from the study and followed clinically.

f. Subject must have been off of any antidepressants for at least one week.

- Laboratory determinations to include standard hematology, and blood chemistry.
- g. h. If subject is female of childbearing potential, a urine pregnancy test will be performed in the office at screening.

Performed on a subset of subjects at participating sites, j. Adverse events occurring prior to randomization will be recorded as part of each patient's medical history. Those AEs occurring following the first TMS treatment session through 30 days after last study visit will be collected.

Medication treatment for emergent insomnia and emergent anxiety is permitted (refer to protocol for usage allowance). Refer to Appendix D for the Concomitant Medication List. k.

In addition to the indicated day, Motor Threshold Determination (MT) may be repeated at any time during the course of the active TMS treatment sessions based on clinical assessment of the Ι. supervising physician. Justification for the additional MT must be documented and pre-approved by the Sponsor when possible.

m. Taper occurs only if exiting the study or transitioning directly to Phase III.

44-02219-204, Rev C 21-JAN-2019

#### Phase II:

Phase		6-Week 3-Week Open Label Acute Treatment Post-Treatment Taper i					aper i		
Week	Wk 1 b	Wk 1 b Wk 2 b Wk 3 b Wk 4 b Wk 5 b Wk 6 b,c /ET         Wk 1         Wk 2						Wk 2	Wk 3
Day(s)	1-5	8-12	15-19	22-26	29-35	36-42	43-49	50-56	57-63
Informed Consent/Assent	X a								
Efficacy Assessments d									
HAMD 24 /MADRS				Xd		X c,d			x
CDRS-R				Xd		X c,d			x
CGI-S				Xď		Xc,d			х
QIDS-A17-SR				Xď		X c,d			х
Neuropsychological Assessments d									
NIH Toolbox Cognition Battery						X c,d			
Safety Assessments									
Vital Signs						Xc			
C-SSRS d	Xd	Xq	Xď	Xď	Xď	X c,d	Xď	Xď	X c,d
YMRS d						X c,d			
Structural MRI e						х			
Audiometry assessment						Xc			
Adverse Events f		х							X
Concomitant Treatment g		х							X
Motor Threshold Determination	X h								
TMS Treatment Session a (daily × 5 weekdays/week)	XXp	XX b	XX b	XX b	XX b	ХХь			
Post-Treatment Taper TMS Session(s) i (3X/Wk1, 2X/Wk 2, 1X/Wk 3)							x	x	x

a. An Informed Consent/Assent for this study must be signed prior to initiating any study-related procedures.

b. The first visit during each week of treatment should occur on a Monday, with daily treatment sessions occurring on Monday through Friday of each week.

- c. Subjects who prematurely discontinue should complete all Week 6 procedures within 2 days after their last TMS treatment session.
- d. Efficacy, neuropsychological and safety assessments to be performed after last TMS treatment session on last day of the treatment week when assessments are required. YMRS to be completed if symptom indicating mania occurs. If positive, a M.I.N.I./KID must be repeated to determine if subject meets full DSM-5 criteria for mania or hypomania. If positive, subject to be discontinued from the study and followed clinically.
- e. Performed on a subset of subjects at participating sites
- f. Adverse events occurring prior to randomization will be recorded as part of each subject's medical history. Those AEs occurring following the first TMS treatment session through 30 days after last study visit will be collected.
- g. Medication treatment for emergent insomnia and emergent anxiety is permitted (refer to protocol for usage allowance). Refer to Appendix D for the Concomitant Medication List.
- h. Motor Threshold Determination (MT) is to be performed prior to the administration of the first active TMS treatment session. In addition, MT may be repeated at any time during the course of the active TMS treatment sessions based on clinical assessment of the supervising physician. Justification for the additional MT must be documented and pre-approved by the Sponsor when possible.
- i. Taper occurs at end of acute treatment and prior to entry into Phase III..

44-02219-204, Rev C 21-JAN-2019

#### Phase III:

Phase				Month m follow up		
Timepoint	Month 1	Month 2	Month 3	Month 4	Month 5	Month 6/ET b
Day(s)	Taper-30	Day 60	Day 90	Day 120	Day 150	Day 180
Informed Consent/Assent	Xa					
Efficacy Assessments c,h						
HAMD 24 /MADRS			x			x
CDRS-R			x			x
CGI-S	х	x	x	х	х	x
QIDS-A17-SR	х	х	x	х	х	x
Neuropsychological Assessments						
NIH Toolbox Cognition Battery						x
Safety Assessments						
Vital Signs						x
YMRS d						
C-SSRS e						
Structural MRI f						x
Audiometry Assessment g						х
Adverse Events h,i	X					Х
Concomitant Treatment h,j	X					Х
Motor Threshold Determination k						
TMS Retreatment ,c, ,e,l (5x/week for 6 weeks)						
See protocol text for description of retreatment parameters						

a. An Informed Consent/Assent for this study must be signed prior to initiating any study-related procedures.

- b. Subjects who prematurely discontinue should complete all Month 6 procedures within 2 days after their last TMS treatment session.
- c. TMS retreatments should begin on a Monday, with daily treatment sessions occurring on Monday through Friday of each week. All efficacy and safety assessments must be completed prior to the start of retreatment. Efficacy assessments must be completed every other week during each TMS retreatment with the assessment beings conducted after the last treatment for the two-week block. TMS treatment to stop when the CGI-S value returns to the Phase III entry score or a full 6 weeks of TMS treatment has been completed. A 3-week taper should follow each retreatment session. TMS retreatment can occur multiple times if symptom re-emergence occurs.
- d. Y-MRS to be completed if symptom indicating mania occurs. If positive, a M.I.N.I./M.I.N.I. KID must be repeated to determine if subject meets full DSM-5 criteria for mania or hypomania. If positive, subject to be discontinued from the study and followed clinically.
- e. C-SSRS to be performed after last TMS retreatment session on last day of the retreatment week.
- f. Performed on a subset of subjects at participating sites.
- g. Audiometry assessments must be performed immediately prior to the start of the TMS retreatment and at the completion of the retreatment course.
- Efficacy assessments to be performed the end of each month for monthly visits. Subjects will be called to assess safety and well-being between visits at
  approximately 2 weeks post previous months visit.
- i. Those AEs occurring following informed consent signature through 30 days after the last study visit will be collected.
- j. Medication treatment for emergent insomnia and emergent anxiety is permitted (refer to protocol for usage allowance).
- k. A Motor Threshold Determination (MT) is to be performed prior to the administration of the first TMS treatment in each treatment course. In addition, motor threshold may be repeated at any time during the course of the active TMS treatment sessions based on clinical assessment of the supervising physician.
- I. TMS retreatment is to occur if the CGI-S increases by 1 from the score at entry into Phase III and is confirmed one week later.

44-02219-204, Rev C 21-JAN-2019

#### C. Study Populations:

Efficacy outcomes will be computed as described in the sections below for both the intent-to-treat and perprotocol study populations in order to demonstrate the generalizability and consistency of the study findings. Safety analyses will be conducted on all enrolled population.

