Objectives	To evaluate the durability of benefit of TMS treatment over the course of 6 months in subjects who received clinical benefit from acute treatment course(s) (Phase III).
	To evaluate the benefit of daily, active, open-label TMS in Phase I subjects who did not receive protocol-defined clinical benefit; as new acute treatment (sham to active) or as extended treatment course (blinded active to open label active) (Phase II)

	Structural MRI (conducted at specific sites only): To utilize standard morphometric measures to determine structural changes in the brain associated with TMS treatment.
	Phase I: Total of 100 enrolled (50 Active/50 Sham) across sites
Number of Subjects	 Phase II: Subjects from phase I who did not receive protocol-defined clinical benefit from acute treatment will be offered open-label treatment (estimated to be 42 subjects) Phase III: Subject who did meet protocol-defined clinical benefit after acute treatment in Phase I or Phase II will be followed for 6 months post taper (estimated to be 37 subjects) Structural MRI subset: Approximately 25% of subjects of the Phase I population.
Diagnosis and Main Inclusion Criteria	 Male or female outpatients, age 12-21, meeting DSM-5 diagnosis of Major Depressive Disorder, single or recurrent course of illness, of moderate or greater symptom severity CGI-S score ≥ 4 HAMD₂₄, item 1 ≥ 2 and total score at least 20 at screening At the end of the baseline visit, subject must have a HAMD24 score of ≥ 18 and change in score may not be ≥ 25% decrease from that seen at the screening visit Duration of current episode of depression ≥ 4 weeks and ≤ 3 years Resistance to antidepressant treatment in a discrete illness episode defined by the Antidepressant Treatment Record (ATR): Resistance to treatment defined by ATR level 1 through 4 in current episode. If insufficient number of trials in a previous episode Subjects who have been unable to complete an antidepressant trial of adequate dose and duration due to intolerance to antidepressant therapy may be included if they have demonstrated intolerance to ≥ 4 antidepressant medications within one discrete illness episode (current or a previous episode as defined above) For any subject currently receiving antidepressant medication, the clinician must determine that insufficient benefit is being received from this treatment and it is clinically appropriate to discontinue the existing antidepressant.

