#### 1. All Enrolled Population:

The all-enrolled study population is defined as those individuals who signed an informed consent, and were subsequently randomized in the study (this population includes both the evaluable and the non-evaluable patient samples). The reasons for patient non-evaluability will be itemized in the final study report, however, no other summary statistics of demographics or clinical outcomes will be reported for the all-enrolled study population. This population will constitute the safety analysis dataset.

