#### 2. Intent-to treat/Evaluable:

The intent-to-treat study population (also known as the evaluable patient population) is defined as all subjects who signed an informed consent, were enrolled in the study and received at least one treatment (whether partial or complete), and for whom a complete post-baseline observation is available for analysis in Phase I.

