#### **B.** Reasons for Discontinuation

All enrolled patients should have a disposition recorded on the termination record, and this should be summarized in tabular fashion listing the proportion of patients discontinued and the recorded reason for discontinuation at the specific study stage listed above. Reasons for termination from the study as captured on the termination record are listed in Table 6. The number of patients whose data are missing, but the patient is not dropped from study; at each specific study stage should be indicated.

Table 4. Reasons for Study Termination

Reason for Study Termination	
Non-Evaluable	
No TMS treatment received	
No post-baseline assessments obtained	
Study Complete	
• Phase 1 complete (number of weeks of treatment)	
• Enrolled in Phase II	
Completed Phase II	
• Enrolled in Phase III	
Completed Phase III	
Study Not Complete (reason given)	
Satisfactory response – efficacy	
• Adverse event (specified on AE form)	
• Failed to return	
Unsatisfactory response – efficacy	
Patient request	
• Other (specified on termination record)	

Upon inspection of the proportion of reasons for discontinuation, a separate listing of the verbatim reasons categorized as 'Other' may be performed.

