## **B.** Adverse Event Reporting:

The general methodology for adverse event collection is discussed in the study protocol. All verbatim reported adverse events are coded using the current version of the Medical Dictionary for Regulatory Activities (MedDRA). All adverse events are categorized by the investigative site staff by severity (3-tier) and by relatedness to the study device (5-tier).

Protocol-emergent adverse events will be reported separately for the Phase I, Phase II, the taper phase, and Phase III. For each study phase, tabular display of adverse events should be provided as follows:

- 1) Adverse events by system organ class and preferred term
- 2) Adverse events by system organ class, preferred term and severity
- 3) Adverse events by system organ class, preferred term and relationship to study device.

44-02219-204, Rev C 21-JAN-2019

Page 21 of 28

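### The only safety set is everyone randomised, treated or not, and the by-phase adverse event tables have no stated denominator

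*SAP*

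**What the plan says.** SAP Section 3.C (Study Populations) states: "Safety analyses will be conducted on all enrolled population". Section 3.C.1 defines that population as "those individuals who signed an informed consent, and were subsequently randomized in the study", says that it includes both evaluable and non-evaluable patients, and adds: "This population will constitute the safety analysis dataset". No other safety set is defined in either document.

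The reasons for termination in SAP Section 5.B include, under the non-evaluable heading, "No TMS treatment received". An exposure condition appears in the intent-to-treat definition (Section 3.C.2), which covers patients who "were enrolled in the study and received at least one treatment (whether partial or complete") and who have a post-baseline observation. The safety set has no such condition.

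SAP Section 8.B says: "Protocol-emergent adverse events will be reported separately for the Phase I, Phase II, the taper phase, and Phase III". It specifies the breakdowns (organ class, preferred term, severity, relationship) but not the denominators.

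The adverse event footnote to the Phase I schedule, in SAP Section 3.B and Protocol Appendix A, reads: "Those AEs occurring following the first TMS treatment session through 30 days after last study visit will be collected". Protocol Section 16.3 and the Phase III schedule footnote start collection at consent instead.

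The Protocol Study Summary (Section 7) plans 100 patients in Phase I, 50 per arm. Of these, Phase I patients without protocol-defined benefit "will be offered open-label treatment (estimated to be 42 subjects"), and an estimated 37 patients will be followed in Phase III.

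**The concern.** An adverse event rate describes risk among people who were exposed. Two features of the plan work against that.

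- A patient who was randomised but never treated belongs to the safety set. Under the Phase I footnote, that patient cannot contribute a collected event.
- Phase II, the taper and Phase III are each entered by only some of those randomised, yet the one defined safety set takes no account of who entered.

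Safety is part of the primary objective in Protocol Section 9.1, and acute and long-term safety are secondary objectives in Protocol Section 9.2 and SAP Section 1.C. Phases II and III carry the extended exposure: up to 66 active treatments across Phases I and II, and up to 72 more in Phase III (SAP Sections 3.A.2 and 3.A.3). A denominator larger than the exposed group would make the device look safer than the data show, and most of all in those later phases.

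**Working it through.** **Inputs**

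- Randomised: 100, 50 per arm (Protocol Section 7).
- Expected entrants: 42 in Phase II and 37 in Phase III (Protocol Section 7). No response or continuation rate is given behind these estimates, so they cannot be re-derived and are used as stated.
- Illustrative rate: application site pain in the adult trial (Protocol Section 8.4, Table 1). It recomputes: 59/165 = 35.8% active and 6/158 = 3.8% sham.
- Number never treated: not given. Assumed range 0 to 5 of 50 per arm (0 to 10%).

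**Formula**

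Reported rate = rate among exposed × (number exposed ÷ number in the safety set). This assumes that unexposed patients contribute no events.

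**Phase I: never-treated patients in the denominator**

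| Never treated of 50 | Calculation | Reported rate |
|---|---|---|
| 0 | 35.8 × 50/50 | 35.8% |
| 1 | 35.8 × 49/50 | 35.1% |
| 2 | 35.8 × 48/50 | 34.4% |
| 3 | 35.8 × 47/50 | 33.7% |
| 5 | 35.8 × 45/50 | 32.2% |

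The relative understatement equals the never-treated fraction, 0 to 10% over this range.

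**Phases II and III: only if the single safety set is used literally**

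- Multipliers: 42/100 = 0.42 and 37/100 = 0.37.
- A 10% rate among entrants would read 10 × 0.42 = 4.2% in Phase II and 10 × 0.37 = 3.7% in Phase III.
- A 35.8% rate would read 15.0% and 13.2%.
- With zero events, the one-sided 95% upper bound is 1 − 0.05^(1/n): 6.9% for n = 42, 7.8% for n = 37, and 3.0% for n = 100.

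No multiplier can be computed for the taper. Patients who go from Phase I to Phase II skip the Phase I taper, and the documents give no count of those who receive it.

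**When collection starts**

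The zero-event assumption for never-treated patients depends on which start rule applies. The Phase I footnote records events before randomisation as medical history and collects events after the first session, so it does not cover the interval between. Protocol Section 16.3 and the Phase III footnote count from consent. Section 8.B tabulates protocol-emergent events, a term neither document defines; Protocol Section 16.1 defines treatment-emergent events instead. These passages need to be reconciled.

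**The case against.** The strongest reply is that naming a safety dataset does not fix the denominator of every table. Section 8.B gives none, and other parts of the SAP do not fit a uniform denominator of 100. Audiometry (Section 8.J) is reported according to participation in each phase, with the sample size shown. The MRI assessment (Section 8.I) covers only some sites. Sections 5.A and 5.B require a disposition diagram for each phase and counts of Phase II and III enrolment. A reader might infer that the plan orders Phase II and III rates to be divided by all randomised patients and so more than halves them. The documents do not support that: it is a possible literal reading, and dividing by phase entrants is the more natural one. What remains is that nothing tells the programmer which to use. The wording in Section 4.B about subjects entering Phases II and III covers illness descriptors only.

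A second reply is that motor threshold determination comes before treatment and is needed for eligibility, so every randomised patient should already have received some stimulation. That is a fair reason to report their events. It does not justify counting them in the denominator of a treatment-session rate.

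A reader might also infer that never-treated patients cannot have any adverse event. That holds only under the Phase I footnote, not under Protocol Section 16.3.

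Regrouping Phase I by coil actually received would add little, because the device stays inactive if the wrong coil is fitted (Protocol Section 13.4).

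Finally, Phase II and III efficacy analyses are descriptive (Section 7.A), serious events are listed individually with narratives (Section 8.C), and entry counts will be available. These limit the harm, but a reader should not have to recompute the rates.

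**Conclusion.** The point holds in two parts of different certainty.

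1. The safety set includes randomised patients who received no TMS session. This is explicit in the SAP. The effect on Phase I rates is small, 0 to 10% in relative terms for an assumed 0 to 10% never treated (35.8% falling to 32.2% at most in the illustration). It requires the Phase I rule that collection starts at the first session.
2. The by-phase adverse event tables have no stated set or denominator. This is an omission. The factors of 0.42 and 0.37 are conditional on applying the single safety set literally and on the planning estimates of 42 and 37. They show what is left to the programmer's choice, not what the plan prescribes.

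This is a clarification worth making before the tables are programmed. It does not touch the efficacy analyses.

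**What to change.** In SAP Sections 3.C and 8.B:

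- Define the safety set as randomised patients who received at least one full or partial TMS session.
- For each by-phase table, state the denominator: patients with at least one session in Phase I, in Phase II or in the taper, and for Phase III the patients who entered it. Print that N in the table.
- List separately any events in patients who were randomised but never treated.
- Reconcile the start of adverse event collection across the Phase I and Phase III schedule footnotes and Protocol Section 16.3, and define protocol-emergent.

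The first three changes alter SAP wording only and need no new data. Never-treated status and phase entry are already recorded on the termination record (SAP Section 5.B), and session details are already entered in the study database (Protocol Section 17.3). Sample size, conduct and efficacy analyses are unaffected, so this is a free improvement. Reconciling the start of collection may also need a clarifying line in the Protocol.
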